Soluble Protein	X			X		X	X	X			X
PAXGene RNA for expression analysis in whole blood	X			X		X		X			
Genetics	X										
Archived samples [serum; plasma]	X			X		X		X		X	

Assessments	Day -7 to Day -1	D1	D4	D8	D11	D15	D22	D29	D36	D43	D50
	Week-1 (Baseline)	W1	W1	W2	W2	W3	W4	W5	W6	W7	W8
Optional Assessments											
Urine or serum pregnancy test ⁷		X									
Optional: fine needle aspiration of liver ⁸									X	X	X
Optional: PBMC Collection for immunophenotyping ⁹									X	X	X
Optional: Soluble Protein ⁹									X	X	X
Optional: PAXGene RNA for expression analysis in whole blood ⁹									X	X	X

1. Dosing to occur only after the completion of all assessments to determine dosing is safe to proceed
2. Women of childbearing potential (WOCBP) must have both:
 - a. A confirmed menstrual period prior to the first dose of study intervention; additional evaluation (e.g., amenorrhea in athletes, birth control) should also be considered
 - b. AND a negative highly sensitive pregnancy test [urine or serum] before the first dose of study treatment
3. Hematology- platelet count to be analyzed at local laboratory prior to dose; hematology samples to be collected for central laboratory assessments in parallel
4. PK samples are to be taken pre-dose
5. FNA will only be collected if the investigator deems it appropriate
6. Within 3 hours after study treatment dosing in Week 3 and Week 5. Sample not to be collected if the participant has already withdrawn from treatment.
7. Only to be conducted for women of child-bearing potential if the Screening serum hCG pregnancy test was >24 hours pre-dose first dose.
8. An optional additional FNA may be collected anytime between Week 6 and Week 36 following discussion between investigator and medical monitor based on unexpected changes in HBsAg or ALT. Only 1 additional FNA may be collected for each participant.
9. Only to be collected if the optional FNA is collected at this visit and has not already been collected as part of the standard assessments.

Table 3 On-Treatment Day 57 to Day 78

Assessments	D57 W9	D64 W10	D71 W11	D78 W12
Window		\pm 3 days		
Study treatment dosing	X	X	X	X
Safety Assessments				
AE/SAE review	X	X	X	X
Concomitant medication review	X	X	X	X
Symptoms directed exam	X			
Vital signs	X	X	X	X
Injection site reactions	X	X	X	X
Laboratory				
Pregnancy test (women of child bearing potential)	X			
Hematology ¹ [includes platelet count and WBC with differential]	X	X	X	X
PT, INR, aPTT	X			
Chemistry	X	X	X	X

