2.3.1. Risk Assessment

Risks are summarized in [Table 5](#). Additional withdrawal/stopping criteria for liver chemistry, drug induced vascular inflammation (DIVI), hematology, renal function, and PK are discussed in [Section 7](#).

Table 5 Summary of Potential Risks of Clinical Significance

Potential Risk of Clinical Significance	Summary of Data/Rationale for Risk	Mitigation Strategy
Investigational Product (IP) [e.g., GSK3228836]		
Nonclinical Risks: Drug Induced Vascular Inflammation and Complement Activation	Inflammatory and immune changes are recognized as a class effect of antisense oligonucleotides (ASOs). Vasculitis and/or perivascular inflammation has been described in monkey studies with many if not most ASOs. This effect has not been observed in clinical studies with GSK3228836 to date.	Laboratory Evaluations: Inclusion of biomarker panels to look for inflammatory and immune activation that would be expected to accompany vascular inflammation Stopping Criteria: Proposed Monitoring Schedule and Stopping Rules for Drug Induced Vascular Inflammation and Complement Activation (see Section 7.1.2)
Clinical Risks:		
Drug induced liver injury / ALT Flares	The liver is a site of accumulation of antisense oligonucleotides. Liver findings in nonclinical studies of GSK3228836 were generally limited to mild hepatic enzyme elevations associated with hepatic vacuolation without concomitant histologic evidence of degeneration in mice, consistent with findings noted with other 2'-methoxyethyl (MOE) ASOs. Review of the available clinical data indicates liver enzymes are increased on treatment with ASOs in a low percentage of patients compared to placebo. ALT elevations (defined as ALT $\geq 2X$ ULN) associated with HBsAg reductions were observed in 8 out of 18 treatment-naïve participants in the ISIS 505358-CS3 study [150 mg GSK3228836, N=6; 300 mg GSK3228836, N=12]. Among the 8 participants with ALT flares, 6 achieved >1 log HBsAg reduction, another 2 had >0.5 log HBsAg reduction.	Laboratory Evaluations: hepatic enzyme monitoring as presented in Table 7 Stopping Criteria: ALT flares are expected in the study population. Monitoring and stopping criteria are presented in Section 7.1.1

Potential Risk of Clinical Significance	Summary of Data/Rationale for Risk	Mitigation Strategy

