Where liver biopsies were once considered routine in the diagnosis and monitoring of liver disease in patients with CHB, they have been mostly replaced by non-invasive tests in recent years, limiting the opportunity to study the liver-resident immune subpopulations in clinical studies. Research papers have recently described the use of fine needle aspirates (FNAs) as a rapid and better-tolerated alternative to conventional core biopsies for sampling intrahepatic immune cells, including T-cells and cells of the innate immune system, such as liver-resident NK cells. This novel technique has been shown to be safe and effective for repeat sampling of the same patient over several weeks/months, permitting longitudinal analysis of immune responses to therapeutic interventions in clinical trials for the first time [Gill, 2019; Tjwa, 2016; Sprengers, 2005].

In study 212602, it is proposed to perform a total of 5 FNAs at preselected timepoints (plus up to 1 optional FNA) during the 45-week study duration (see Section 1.2). The timing of FNAs has been selected to assess intrahepatic immunological changes at different stages of treatment with GSK3228836, and in the follow-up period (Table 6)

Table 6 Timepoints for Fine Needle Aspirates

FNA number	Time point (Study Week)	Description
1	Week -1	Baseline sample
2	Week 3	Early on-treatment. Preceding anticipated marked declines in serum HBsAg level.
3	Week 5	Anticipated start of HBsAg level <LLOQ in responders and start of ALT flare (Based on review of efficacy data in study ISIS 505358-CS3).
4	Week 13	End of treatment
5	Week 36	End of follow-up
6 (Optional)	Any between Week 6 and Week 36	To be determined following discussion between investigator and medical monitor. May be triggered by changes in serum HBsAg levels or ALT.

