7.1.1. Liver Chemistry Monitoring and Stopping Criteria

Liver chemistry stopping, and increased monitoring criteria have been designed to assure participant safety and to evaluate liver event etiology. Study intervention will be discontinued for a participant if the liver stopping criteria are met.

Discontinuation of study intervention for abnormal liver tests is required when:

- a participant meets one of the conditions outlined in [Table 7](#).
- when in the presence of abnormal liver chemistries not meeting protocol-specified stopping rules, the investigator believes study intervention discontinuation is in the best interest of the participant.

[Table 7](#) lists the criteria for withholding or discontinuing the study medication in a study participant with elevation of ALT. Additional testing will be performed (see safety follow-up procedures for participants who meet increased monitoring or stopping criteria), and the participant monitored until liver chemistry abnormalities resolve, stabilize, or return to within baseline values. The participant must then attend the follow-up visits specified in the SoA.

Every attempt must be made to have the participant evaluated (within 24 hours) for repeat assessment of liver chemistries and additional testing and close monitoring (a specialist or hepatology consultation is recommended). Participants must be monitored weekly until liver chemistry abnormalities (ALT, AST, alkaline phosphatase, bilirubin) resolve, stabilize, or return to within baseline values. Upon completion of the safety follow-up procedures (see below), the participant must attend the follow-up visits specified in the SoA.

Table 7 Liver Chemistry Monitoring and Stopping Criteria

ALT Level	Monitoring Plan	Discontinuation
10x ULN ≤ ALT <12x ULN and Bilirubin ≤1.5x ULN and INR ≤1.5 (if available)	Monitor twice weekly Additional lab assessments	Permanently discontinue IMP if ALT >10x ULN >4 weeks
ALT ≥12x ULN and Bilirubin≤1.5x ULN and INR ≤1.5 (if available)	Hold dose Monitor twice weekly Additional lab assessments if not already done Take off hold: 150 mg SC weekly when ALT <10x ULN; increasing dose to 300 mg (if applicable) should be agreed with Medical Monitor	Permanently discontinue IMP if any of the following apply: 
 • ALT ≥10x ULN >4 weeks • ALT ≥12x ULN recurs after IMP taken off hold

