ALT ≥3x ULN and 1.5x ULN <bilirubin ≤2x ULN (>35% direct) and INR ≤1.5 (if available)	Hold dose Monitor twice weekly Additional lab assessments if not already done Take off hold: 150 mg SC weekly when bilirubin returns to <1.5x ULN; increasing dose to 300 mg (if applicable) should be agreed with Medical Monitor	Permanently discontinue IMP if the following recurs after IMP taken off hold: 1.5x ULN <bilirubin ≤2x ULN (>35% direct) And INR ≤1.5 (if available)
ALT ≥3x ULN and any of the following apply: 
 • bilirubin >2x ULN (>35% direct) • associated with the appearance or worsening of hepatitis symptoms • INR >1.5 (if available) 		Permanently discontinue IMP Monitor twice weekly until stable ALT Additional lab assessments if not already done

ALT = alanine aminotransferase; IMP = investigational medicinal product; ULN = upper limit of normal

*Notes:

- Any abnormal laboratory parameters that meet the criteria for individual treatment discontinuation must be confirmed by retest of a new collection of blood samples as soon as possible.

- Any clinically significant deterioration from the baseline in the liver parameters must be confirmed by retesting ALT, total bilirubin, direct bilirubin, and INR (if available).
- If one criterion in the list above is met and confirmed by retesting, further treatment may be discontinued for this participant after discussion with the Medical Monitor. Results of retesting must be evaluated before the next dose is administered.
- Monitor participant until liver chemistry abnormalities resolve, stabilize, or return to within baseline values.
- Cases such as Gilbert syndrome, where baseline bilirubin values are high, should be discussed with the medical monitor, to assess if it is a case of drug-induced liver injury (DILI) or the participant may continue with dosing.

The procedures listed below are to be followed if a participant meets any of the liver chemistry stopping criteria defined in [Table 7](#):

Notify the Medical Monitor within 24 hours of learning of the abnormality to confirm the participant's study treatment cessation and follow-up.

Complete the Liver Event case report form (CRF).

Complete the "Safety Follow-up Procedures" listed below.

Safety Follow-up Procedures for Participants Who Meet Any of The Liver Monitoring and Stopping Criteria:

Viral hepatitis serology including:

- Hepatitis A IgM antibody;
- Cytomegalovirus IgM antibody;

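### No text makes an INR mandatory when on-treatment ALT reaches ≥3x ULN, so the INR >1.5 permanent-stop criterion can go unevaluated while dosing continues

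*Protocol*

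**What the plan says.** The last row of Table 7 (Protocol 7.1.1) orders permanent discontinuation at ALT ≥3x ULN if any one of three further conditions holds: bilirubin above 2x ULN (mostly direct criteria applying), new or worsening hepatitis symptoms, or "INR >1.5 (if available"). The milder rows carry the same qualifier. The lowest ALT band with any action at normal or near-normal bilirubin is "10x ULN ≤ ALT <12x ULN and Bilirubin ≤1.5x ULN and INR ≤1.5 (if available"), and it brings closer monitoring without a dose hold.

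Two rows hold the dose. Their restart rules are "Take off hold: 150 mg SC weekly when ALT <10x ULN" and "Take off hold: 150 mg SC weekly when bilirubin returns to <1.5x ULN". Neither mentions INR.

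One Table 7 note is event-driven and names INR. A clinically significant worsening of liver parameters from baseline "must be confirmed by retesting ALT, total bilirubin, direct bilirubin, and INR (if available"). Another note has retest results evaluated before the next dose.

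The follow-up lists in 7.1.1 and Appendix 6, the Appendix 2 list of liver follow-up tests, and the analytes named in 7.1.1 for weekly monitoring do not include INR.

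On timing, Table 5 states that "ALT flares are expected in the study population". Table 6 describes Week 5 as "Anticipated start of HBsAg level <LLOQ in responders and start of ALT flare".

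**The concern.** A stopping criterion works only if the quantity it uses is measured when the decision is made. ALT and bilirubin are measured at every weekly dosing visit from Week 5. INR is not, and the availability qualifier lets an absent INR pass as an acceptable one.

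In a flare during Weeks 6 to 8 or 10 to 12, a site could follow the plan exactly and keep dosing a participant whose INR, if drawn, would have required a permanent stop and an SAE report under Section 10.3.2. The SAP (Section 4.5.3.1) summarises liver stopping events and increases in INR to Grade 3 or higher. An INR that was never drawn cannot appear in either summary.

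**Working it through.** The plan gives no figure to reproduce. The check is a count of scheduled visits, a reading of the text, and a workload estimate.

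**1. Scheduled draws (Protocol 1.3, Tables 2 to 4), from Week 5 to the last dose**

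| Day | 29 | 36 | 43 | 50 | 57 | 64 | 71 | 78 |
|---|---|---|---|---|---|---|---|---|
| Chemistry (ALT, bilirubin) | X | X | X | X | X | X | X | X |
| PT/INR | X | – | – | – | X | – | – | – |
| Haematology with local pre-dose platelets | X | X | X | X | X | X | X | X |

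- From Week 5: INR at 2 of 8 visits = 25%.
- From Week 6: 1 of 7 (Day 57).
- All on-treatment chemistry visits after Day 1 (Days 8, 15, 22, 29, 36, 43, 50, 57, 64, 71, 78): INR on Days 15, 29 and 57, so 3 of 11 = 27%.
- Nominal gaps: 57 − 29 = 28 days and 85 − 57 = 28 days. From the last on-treatment INR to the last dose: 78 − 57 = 21 days.
- Off treatment, PT/INR is drawn at every visit from Day 85 to Day 246 and at early termination.

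**2. What happens if no INR is known (Table 7)**

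| State | Action | INR assured? |
|---|---|---|
| ALT 3 to <10x ULN, bilirubin ≤1.5x ULN, no symptoms | No row applies; dosing continues | No |
| ALT 10 to <12x ULN, bilirubin ≤1.5x ULN, no symptoms | Twice-weekly monitoring, additional tests; dosing continues | No; the work-up lists omit it |
| ALT ≥12x ULN, or ALT ≥3x ULN with bilirubin >1.5 to 2x ULN | Dose held; restart at 150 mg on ALT or bilirubin alone | Normally requested by the retest note, but subject to availability |
| ALT ≥3x ULN with bilirubin >2x ULN or symptoms | Permanent stop | Not needed for the stop |

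The exposed states are the first two rows.

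**3. How often an added INR rule might be triggered**

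In the earlier study (Protocol 4.2 and 4.3), two of five nucleos(t)ide-treated participants on 300 mg reached HBsAg below LLOQ, and both then had ALT >3x ULN. The documents do not report this for the other three, so two is a minimum.

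- Proportion: 2/5 = 40%. The exact 95% interval runs from the 2.5% point of Beta(2, 4) to the 97.5% point of Beta(3, 3), which is 5.3% to 85.3%.
- Scaled to 20 participants: 0.40 × 20 = 8, with a range of 0.053 × 20 ≈ 1 to 0.853 × 20 ≈ 17.
- Assume 1 to 6 flare visits each without a scheduled INR (6 = Days 36, 43, 50, 64, 71, 78). Draws: 8 × 1 = 8 to 8 × 6 = 48. Over the interval: 1 × 1 = 1 to 17 × 6 = 102.

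This is workload, not missed cases. Timing is also an assumption: both rises followed HBsAg loss on Day 23 or Day 36, after the last injection on Day 22 of that study. They would fall on treatment here only if timing from first dose carries over.

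**The case against.** The strongest reply is that the plan already orders the test. The retest note is mandatory in form and names INR. Entry requires ALT ≤2x ULN, so ALT ≥3x ULN is always above the entry limit and could trigger it. This stands against one tempting inference: a reader who looks only at the work-up lists might conclude that no text orders an INR at all, and that would be wrong. The note still does not close the gap. Where flares are expected, whether a rise is clinically significant is a judgement, and the availability qualifier lets the retest be completed without INR.

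The qualifier might refer only to late results, since Appendix 2 has local results used when central ones are not ready in time. The text does not settle this. Under that reading, removing the qualifier costs the sponsor nothing.

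A reader might also infer that restart after a hold is an equal gap, because the restart rules ignore INR. That is too strong. ALT ≥12x ULN, or ALT ≥3x ULN with raised bilirubin, would normally count as clinically significant, so the retest note would apply. The permanent-stop row also still governs while ALT is ≥3x ULN.

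Nor do Section 10.3.2 and Appendix 2 note 3 conflict in effect. The note makes SAE reporting conditional on a measured INR and 10.3.2 does not, but an unmeasured INR cannot exceed 1.5, so the reporting duty is the same.

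Other safeguards remain:
- the bilirubin and symptom criteria
- evaluation within 24 hours, with hepatology advice recommended
- investigator discretion to stop or to add tests
- exclusion of INR >1.25 at entry, and the ban on anticoagulants.

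They narrow the gap but do not ensure that an INR exists when Table 7 needs one.

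**Conclusion.** The point holds in a limited form. The plan makes INR >1.5 with ALT ≥3x ULN decisive, but it does not ensure a value, and PT/INR follows a 4-weekly schedule in the period when flares are anticipated. The main exposure is ALT 3 to <12x ULN with bilirubin ≤1.5x ULN and no symptoms. It is confined to the dosing period, because every follow-up visit has a scheduled INR.

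The count of 2 in 8 visits measures scheduled opportunity. It is not a rate of missed stops: missed cases are probably few, and the documents give no INR data from which to estimate them. The case for change rests on a serious possible consequence and a small remedy, and on the assumption that some flares here will occur on treatment, as Table 6 anticipates. It is worth correcting, but it does not mean that liver monitoring as a whole is inadequate.

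**What to change.** Change no threshold.

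1. In Section 7.1.1, require an INR whenever on-treatment ALT is ≥3x ULN and none was drawn at that visit, including before restart from a hold while ALT is still ≥3x ULN. Draw it at the ALT retest, or at the latest at the next dosing visit. Delete the availability qualifier from the retest note. Use a local result if the central one is late, and review it under the existing rule that retest results are evaluated before the next dose.
2. Add INR to the liver work-up lists in Section 7.1.1, Appendix 2 and Appendix 6.

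Appendix 2 note 3 needs no edit.

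**Cost.** One coagulation tube per flare visit without a scheduled INR, or two when a local result is used, because Appendix 2 asks for a parallel central sample. On the assumptions above this is about 8 to 48 draws (1 to 102 over the interval). Twice-weekly monitoring at ALT ≥10x ULN could add some. Item 1 is a small new dosing gate, and it falls on participants with flares, who may be the responders, so an occasional short dose delay is possible. The delay is limited because these visits already require the "platelet count to be analyzed at local laboratory prior to dose". Home-nursing visits need a route to a local INR result. Drawing INR at all 8 chemistry visits that lack it would take 8 × 20 = 160 draws and is not needed.

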7. DISCONTINUATION OF STUDY INTERVENTION AND PARTICIPANT DISCONTINUATION/WITHDRAWAL

7.1. Discontinuation of Study Intervention

A participant may withdraw from the study treatment at any time at his/her own request or may be withdrawn at any time at the discretion of the Investigator for safety, behavioural or administrative reasons. In rare instances, it may be necessary for a participant to permanently discontinue (definitive discontinuation) study intervention. Participants that withdraw from treatment for any reason should be encouraged to complete all their on-treatment and follow-up visits and assessments. Should the participant not wish to continue with weekly visits in the on-treatment window, a reduced visit schedule may be considered. The reduced visit schedule should include Weeks 3, 5 and 12 and all specified assessments as a minimum. Every effort should be made to complete the early termination (ET) study procedures and observations if the participant does not enter post-treatment follow-up.

Any laboratory parameter that meets the stopping criteria should be repeated to confirm the value prior to withdrawal

For participants meeting the stopping criteria (Section 7.1.1- Section 7.1.4), participants should be monitored until laboratory abnormalities resolve, stabilize, or return to within baseline values (i.e., pre-dose) as indicated. The participant must then attend the visits specified in the SoA. See the SoA for data to be collected at the time of discontinuation of study intervention and follow-up and for any further evaluations that need to be completed.

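### A note under Table 7 makes stopping optional after a confirmed liver criterion and does not exempt the permanent-stop criteria, which Section 7.1.1, Table 7 and Appendix 6 treat as mandatory

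*Protocol*

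**What the plan says.** **Mandatory wording.** Section 7.1.1 opens with "Study intervention will be discontinued for a participant if the liver stopping criteria are met". It continues: "Discontinuation of study intervention for abnormal liver tests is required when" a participant meets a Table 7 condition. The last row of Table 7 requires permanent discontinuation when ALT is at or above 3x ULN and any one of three things holds: bilirubin above 2x ULN (over 35% direct), INR above 1.5, or an ALT rise "associated with the appearance or worsening of hepatitis symptoms". Appendix 6 (Section 10.6) directs immediate withdrawal from study treatment when a permanent-discontinuation criterion is met.

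**Permissive wording.** The notes under Table 7 say that when a criterion in the list is "met and confirmed by retesting, further treatment may be discontinued for this participant after discussion with the Medical Monitor". The note does not say which rows it covers.

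**Related text.** Section 7.1.1 and Appendix 6 both ask the site to notify the Medical Monitor within 24 hours, so that cessation of treatment can be confirmed. A separate note sends cases such as Gilbert syndrome, where baseline bilirubin is high, to the Medical Monitor to judge whether dosing may continue.

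**The concern.** A stopping rule has to give one answer when its criterion is met. Here a site that has retested and confirmed the last-row criterion finds an instruction to stop in the table and, beneath it, a note that makes stopping a matter for discussion.

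The ambiguity falls on a situation that this trial can expect to meet. Table 5 says that ALT flares are expected in the study population. Section 4.2 reports that, in the earlier four-week study, both participants on nucleos(t)ide therapy who reached HBsAg below LLOQ then had ALT above 3x ULN, and this trial enrols those thought most likely to respond. The ALT part of the last-row criterion is therefore foreseeable, and bilirubin, INR or symptoms decide whether treatment ends. Section 8.2.9.1 also describes flares as possible evidence of immune clearance, which gives a site a reason to want to continue. At stake is whether a participant with a confirmed sign of severe liver injury could be dosed again within the letter of the protocol.

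**Working it through.** No arithmetic beyond a count applies; the check compares the texts.

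**Step 1: which criteria the note reaches.** Permanent-stop conditions in the discontinuation column of Table 7:

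| Row | Permanent-stop condition | Count |
|---|---|---|
| 1 | ALT above 10x ULN for more than 4 weeks | 1 |
| 2 | ALT at or above 10x ULN for more than 4 weeks; ALT at or above 12x ULN recurring after a hold | 2 |
| 3 | Bilirubin above 1.5x and up to 2x ULN (over 35% direct), INR at most 1.5 if available, recurring after a hold | 1 |
| 4 | ALT at or above 3x ULN with bilirubin above 2x ULN (over 35% direct), with hepatitis symptoms, or with INR above 1.5 | 3 |

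Total: 1 + 2 + 1 + 3 = 7. The note refers to any criterion in the list, so none of the seven is exempt.

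**Step 2: what the other texts require for row 4.**

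| Place | Instruction | Reading |
|---|---|---|
| 7.1.1, opening | "Study intervention will be discontinued for a participant if the liver stopping criteria are met" | mandatory |
| 7.1.1, lead-in to the conditions | "Discontinuation of study intervention for abnormal liver tests is required when" | mandatory |
| Table 7, row 4 | permanent discontinuation, unconditional | mandatory |
| Appendix 6 | immediate withdrawal from treatment | mandatory |
| Table 7 note | "met and confirmed by retesting, further treatment may be discontinued for this participant after discussion with the Medical Monitor" | optional |

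Four statements point one way and one points the other.

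**Step 3: whether the note can be read as deliberate discretion.** Section 7.1.1 already gives the investigator discretion, but only to stop treatment for abnormal chemistries that do *not* meet the stopping rules. A general *may* for values that do meet them would erase that distinction. The other safety sections offer no parallel: 7.1.2, Table 8 and 7.1.4 direct permanent discontinuation once their permanent-stop criteria are established. The Gilbert syndrome note is a separate, narrow exception and would be unnecessary if every stop were optional.

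**Step 4: clinical weight.** Note 3 to Table 11 in Appendix 2 treats ALT at or above 3x ULN with bilirubin at or above 2x ULN (over 35% direct), or with INR above 1.5, as possible Hy's Law and requires SAE reporting. Two of the three row 4 conditions match these almost exactly; the only difference is above versus at or above 2x ULN for bilirubin.

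**Step 5: effect on the analysis.** Under Protocol 9.4.2 and SAP 4.2.1 the primary estimand uses a treatment-policy strategy for discontinuation. Neither reading of the note changes the definition of the response, the sample size or the posterior calculation.

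**The case against.** The strongest defence is that the intent is clear elsewhere. The Medical Monitor is to be contacted to confirm that treatment has ceased, which presupposes that it has. Appendix 6 is confined to permanent-discontinuation criteria and is unconditional. Table 7 mixes monitoring, hold and stop rows, so a general note over all of them might naturally say *may* and leave each row to state its own action. This defence stands as evidence of intent, and it is why the severity is minor. It does not remove the contradiction, because nothing in the note limits it to the monitor and hold rows.

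Three stronger readings are tempting, and the documents do not support them.

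- A reader might infer that 7.1.1 orders a *permanent* stop for every Table 7 row. Its prose says only that treatment is discontinued, and it introduces the table as criteria for withholding or discontinuing. Row 1 starts with closer monitoring, and rows 2 and 3 start with a hold.
- A reader might infer that Appendix 6, by calling for immediate withdrawal without mentioning a retest, conflicts with the confirmation rule. It takes its criteria from 7.1.1, where abnormal results that meet them "must be confirmed by retest of a new collection of blood samples as soon as possible" and where "Results of retesting must be evaluated before the next dose is administered". Section 7.1 adds: "Any laboratory parameter that meets the stopping criteria should be repeated to confirm the value prior to withdrawal". Appendix 6 does not waive any of this, so the texts can be read together.
- A reader might try to count the doses lost to unconfirmed stops. The documents give no rate of unconfirmed values, and the schedule of activities allows dosing only after the assessments that show it is safe, so such a count would rest on assumptions the protocol does not supply.

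**Conclusion.** The note is wrong as written, and the severity is minor. On its literal wording it makes stopping optional for all seven permanent-stop conditions in Table 7, and for row 4 it contradicts the other four statements. The conclusion rests on reading the note's reference to a listed criterion as covering the whole table, which is what the words say. The surrounding text makes a mandatory stop the evident intent, so most sites would probably act correctly; that is a judgement, since the documents give no data on how sites read the note. The consequence is confined to participant safety and uniform conduct across sites, and no efficacy estimate depends on it.

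**What to change.** Replace the note under Table 7 with wording such as: *When a criterion for permanent discontinuation has been met and a retest confirms it, study treatment will be permanently discontinued and the Medical Monitor notified. For the monitor and hold rows, follow the instructions in the row and discuss with the Medical Monitor.* Keep the Gilbert syndrome note as it stands, as the one stated exception.

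The cost is one reworded note in the next amendment. It adds no tests, visits or data collection, and the SAP needs no change.
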